### **Aim 1: To study the effects of resveratrol on age-related insulin resistance**

*We hypothesize that treatment of overweight, middle aged or Type 2 diabetes subjects with resveratrol will result in improved insulin sensitivity, as demonstrated by increased insulin-stimulated glucose uptake and enhanced insulin-mediated suppression of glucose production.*

We will study the following subject group:

- **Overweight and either young or middle aged** (BMI 25-30 kg/m^2, age 21-65) nondiabetic subjects, n=40 diabetic subjects (BMI=25-35) n=15

Each subject will receive a 28 day course of **resveratrol** (n=55). RevGenetics will supply the resveratrol (500 mg capsules; 2 capsules bid) for our proposed studies. A certificate of analysis has been provided by the manufacturer.

A comprehensive study of whole-body insulin action will be undertaken with specially designed „stepped” euglycemic (~90 mg/dl) -hyperinsulinemic clamp studies, both before and after administration of resveratrol.

Thus, we will compare the following parameters under paired conditions in each subject, on day 0 and day 28 of resveratrol treatment:

- a. **hepatic insulin action:** this will be determined as the ability of low infusion rates of insulin (20 mU/m^2.min above basal requirements) to suppress glucose production during the “**low insulin phase**” of the clamp studies.
- b. **peripheral insulin action:** this will be determined as the ability of high infusion rates of insulin (80 mU/m^2.min above basal requirements) to stimulate glucose uptake during the “**high insulin phase**” of the clamp studies.

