### In vivo clamp studies – General Conditions

Subjects will be admitted on the day of the study to the General Clinical Research Center (GCRC) study room after an overnight fast. Subjects with type 2 diabetes will be admitted to the Jack Weiler Hospital of the Albert Einstein College of Medicine the night before the study. All anti-diabetic medications, including insulin, will be held from one day to one week prior to the clamp study date depending on the drug they are taking. They will not eat after 10 PM the night before the study (but can drink water). An intravenous catheter will be inserted into their left arm and insulin will be administered overnight to maintain their glucose at normal levels. Blood samples will be collected every hour for glucose values. At 8:00 am 2 intravenous cannulae will be established, one for infusions and a second one to be inserted in a retrograde fashion in a dorsal vein of the opposite arm for blood sampling. To obtain arterialized venous blood samples, this hand will be maintained at 65°C in a thermoregulated plexiglass box.

[figure not shown]
A primed continuous infusion of D2G-glucose will be initiated at t=-120 min (2 hours prior to the onset of the „clamp” study). A bolus of 200 mg/m^2 D2G for the duration of 3 min will be followed by a continuous infusion of 2 mg/min/m^2 D2G for the entire study in all subjects (for total duration of 6 hours) to **quantify glucose turnover**, specifically rates of peripheral glucose disposal and hepatic glucose production.

These „pancreatic clamp” experiments will consist of 360 min insulin/somatostatin (250 µg/hr) or insulin/octreotide (30 mg/kg/min) infusions with replacement of glucoregulatory hormones (glucagon 1 ng/kgmin; growth hormone 3 ng/kgmin). Throughout the entire 360 min the plasma glucose concentration will be maintained at basal levels (~90 mg/dl).

**Basal phase:** From t=0 min to t=120, optimal insulin infusion rates will be selected in each individual by making frequent (~ every 25 mins) adjustments to the insulin infusion rates in order to establish those insulin infusion rates required to maintain euglycemia (90 mg/dl) without the requirement for exogenous glucose infusion.

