All infusions will be stopped at t=360 min. The patient will be given a standard meal and plasma glucose levels will be monitored at 15-30 min intervals for the next one hour. Dextrose infusion will be continued for approximately 45 minutes after the study in order to avoid hypoglycemia. The patient will be discharged after about one hour, provided that his or her condition remains stable.

**Indirect Calorimetry.** A PARVO MEDICS, (TrueOne® 2400 Metabolic Measurements Systems) will be used to estimate rates of carbohydrate and lipid oxidation from T=260-280 in all studies. Twenty minute averaged values for VO2 and VCO2 will be corrected for nitrogen excretion as urinary urea nitrogen measured enzymatically by the method of Kjeldahl (80). Net glucose and lipid oxidation rates will be calculated from indirect calorimetry. The equations used to calculate glucose and lipid oxidation from gas exchange and urinary urea nitrogen excretion have been published (81). Under conditions in which RQ > 1.0, the overestimation of glucose oxidation will be corrected as described (81).

**Analytical procedures –** Plasma glucose will be measured with a Beckman glucose analyzer (Fullerton, CA) by use of the glucose oxidase method. Measurements of plasma insulin, C-peptide, glucagon, and growth hormone are undertaken throughout the studies in order to evaluate the adequacy of the “pancreatic clamp” technique, ie. inhibitory effects of somatostatin on hormone secretion, and uniformity of hormone replacement. All samples will be kept on ice until centrifuged (within 30 min). Plasma samples will then be sorted and handled by the Special Assay Core, and will be stored frozen at -20°C for later assays. Plasma hormone determinations will be performed by radioimmunoassay as previously reported (82), and these determinations will be provided by the Radioimmunoassay Core of the Diabetes Research and Training Center.

**Substrate determination-** Plasma FFA levels will be determined by using an acyl-CoA oxidase based colorimetric kit (Wako, Osaka, Japan) and glycerol will be measured using colorimetric enzymatic methods (83,84). Plasma lactate will be measured by fluorometric enzyme techniques (85).

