##### **Human Subject Characteristics**

The study population will consist of at least 40 nondiabetic subjects and 15 diabetic subjects with the following characteristics: ages 21-65 years, with BMI between 25 and 30 kg/m^2. The following subjects will be specifically excluded: children, mentally disabled persons, prisoners, pregnant women, fetuses, subjects with a history of ethanol or drug or toxin exposure which could be associated with neuropathy, any subject deemed incapable of giving voluntary informed consent, and subjects with a history of a bleeding disorder or with a prolonged PT or PTT; a history of uterine, breast, or ovarian cancer, renal disease, and liver disease or impairment. Women in the child-bearing age-group will be allowed to participate, provided they have negative pregnancy tests. The research topic to be studied is not relevant to the involvement of special classes or groups of subjects and therefore no criteria for their involvement are specified.

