7. Resveratrol: Resveratrol is present in significant amounts in a variety of foods, including grapes, blueberries, peanuts and red wine and over-the-counter resveratrol supplements are widely used. Formal safety testing is not required for marketing of nutritional supplements, but to date, there have been no published reports of side effects at the commonly used doses (up to 1000 mg /day). A number of *in vitro* studies have demonstrated that resveratrol can be an inhibitor of various cytochrome P450 enzymes that are involved in drug metabolism. The relevance of these *in vitro* observations to *in vivo* use is unclear primarily because oral resveratrol is rapidly metabolized by the liver, free resveratrol levels are quite low and resveratrol metabolites have not been shown to be inducers or inhibitors of CYP enzyme activity. Nonetheless, caution is warranted, especially for drugs with a narrow therapeutic window (anti-epileptics, mexilitene, quinidine, cyclosporine, tacrolimus, HIV protease inhibitors) and use of these drugs will be exclusionary for this study. Furthermore, due to the potential estrogenic effects of resveratrol, a medical history of ovarian, uterine, and breast cancer will be exclusionary for the study.
8. Somatostatin: At the proposed physiological replacement doses has no known side effects.
9. Ocreotide: At the proposed physiological replacement doses has no known side effects.

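### The octreotide rate for the pancreatic clamp is printed as 30 mg/kg/min, which comes to 10.8 g/kg over 360 minutes; the unit cannot be right and needs confirming, probably to ng

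*Combined protocol and SAP*

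**What the plan says.** The section In vivo clamp studies – General Conditions states that the "experiments will consist of 360 min insulin/somatostatin" at 250 µg/hr, "or insulin/octreotide (30 mg/kg/min) infusions with replacement of glucoregulatory hormones". The replacement rates follow in the same sentence: "glucagon 1 ng/kgmin; growth hormone 3 ng/kgmin". The section later stops all infusions at t=360 min.

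Three other places bear on the line, and none gives an octreotide rate:

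- Analytical procedures, in the same section, uses hormone measurements to judge the clamp, including "inhibitory effects of somatostatin on hormone secretion, and uniformity of hormone replacement". The samples are frozen and assayed later.
- Potential Risks, item 9, says "Ocreotide: At the proposed physiological replacement doses has no known side effects" and gives no number.
- A line at the end of the Aim 1 methods says the techniques are approved under two other protocols, 2000-200 and 2006-414. These are not part of the documents.

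**The concern.** Octreotide is one of two named ways of suppressing endogenous hormone secretion during the clamp. The clamp yields the principal endpoint, glucose uptake over the last hour of the high-insulin phase, compared within each subject between day 0 and day 28. The line is therefore an operative dosing instruction. A rate in mg/kg/min stands out beside two ng rates and a somatostatin rate in µg/hr.

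What is at stake is modest. Staff who choose octreotide cannot prepare it from the protocol as printed and must guess the unit or look elsewhere. The stored-sample assays could show poor suppression afterwards but could not catch a wrong rate during the infusion. The risk statement for octreotide also needs a real dose to refer to.

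**Working it through.** **Inputs**

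- Octreotide 30 mg/kg/min, duration 360 min, somatostatin 250 µg/hr: all from one sentence of In vivo clamp studies – General Conditions.
- Body weight: not given. I assume 80 kg, with a range built from BMI limits and assumed heights. Lower end: 25 x 1.50² = 56.25 kg. Upper end: 35 x 1.90² = 126.35 kg. The limit of 35 is the one Aim 1 sets for "diabetic subjects (BMI=25-35) n=15"; Human Subject Characteristics caps BMI at 30, so this is the wider choice.

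The plan states no total octreotide dose, so there is no derived figure to reproduce.

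**Step 1: dose as printed**

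30 mg/kg/min x 360 min = 10,800 mg/kg = 10.8 g/kg, which is 1.08% of body mass at any weight. At 80 kg: 10.8 x 80 = 864 g per clamp.

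**Step 2: the stated alternative**

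Somatostatin: 250 µg/hr x 6 h = 1,500 µg = 1.5 mg per clamp. The printed octreotide dose for each single kilogram of body weight is already 10,800 / 1.5 = 7,200 times that total. At 80 kg the ratio is 864,000 mg / 1.5 mg = 576,000.

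**Step 3: which prefix would fit**

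Keep the 30 and the per-kg-per-minute basis and vary only the prefix. Hourly rate = 30 x weight x 60; at 80 kg this is 144,000 units per hour.

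| Prefix | Rate at 80 kg | Ratio to 250 µg/h | Ratio, 56 to 126 kg |
|---|---|---|---|
| mg (printed) | 144 g/h | 576,000 | 405,000 to 910,000 |
| µg | 144 mg/h | 576 | 405 to 910 |
| ng | 144 µg/h | 0.58 | 0.41 to 0.91 |
| pg | 0.144 µg/h | 0.0006 | 0.0004 to 0.0009 |

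Only ng gives a rate of the same order as somatostatin: 101 to 227 µg/h across the assumed weights. The clamp total would then be 30 ng x 360 = 10.8 µg/kg, or 864 µg at 80 kg.

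**Step 4: what the comparison can bear**

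The ratios compare the masses of two different drugs, and the documents give no potency conversion. That does not matter for rejecting mg, because a dose of about 1% of body mass is impossible by itself. It does matter for choosing ng, which is an inference from order of magnitude and from the neighbouring units.

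**The case against.** The strongest objection is that this may not be an error in the plan at all. It turns on one letter in text extracted from a PDF by machine, and an ng misread as mg would remove the point entirely. This stands as a caveat. Against it, the same sentence shows µg once and ng twice without trouble. A misread µg would not rescue the line either, since that rate is still 405 to 910 times the somatostatin rate.

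Second, a reader might infer that ng is established as the intended unit. The documents do not support that. It follows only if the 30 and the denominator are both correct. The match with glucagon and growth hormone is modest support, because those are replacement hormones, while octreotide's counterpart, somatostatin, is given in µg/hr.

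Third, the line need not be the only dosing source. The two approved protocols cited at the end of the Aim 1 methods may carry the right rate. This is fair, but they are not shown, and the reference leaves the printed figure uncorrected.

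Fourth, a reader might infer a real overdose hazard or a compromised endpoint. Neither is supported. The printed amount could not be prepared, a physician performs the studies, and somatostatin is available at a usable rate. No other figure in the documents is computed from the octreotide rate.

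**Conclusion.** Wrong as written, and minor. The printed 30 mg/kg/min implies 10.8 g/kg per clamp and cannot be the intended rate; this conclusion needs no assumption about weight. That 30 ng/kg/min was meant is probable. It rests on the 30 and the per-kg-per-minute basis being right, on an assumed weight of 80 kg (56 to 126 kg does not change the choice), and on a comparison by mass alone. Whether the slip is in the protocol itself depends on what the source PDF prints.

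The risk statement in Potential Risks, item 9, is not evidence of the error and is not shown to be false; it simply has no usable dose behind it at present. Sample size, power, significance level and analysis are unaffected.

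**What to change.** Check the unit in the source PDF and against the pharmacy order or the approved clamp protocol. If mg is printed, the responsible clinician should confirm the intended rate and correct the line in In vivo clamp studies – General Conditions, probably to 30 ng/kg/min. Potential Risks, item 9, will then refer to a real dose. If the source already prints ng and the order agrees, nothing needs changing.

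The cost is probably one character and one clinical confirmation, with no extra subjects, procedures or analyses.

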**Low phase:** Following establishment of basal insulin requirements during the basal phase, at t=120 the insulin infusion rate will be increased by a fixed increment of 20 mU/m^2/min, and will be maintained at this rate for 2 hours (T=120-240). Plasma glucose will be maintained at euglycemic concentrations (~90mg/dl) by a variable infusion of 20% dextrose for the entire study (78).

**High phase:** At t=240 min, insulin infusion rate will be increased to 80 mU/m^2/min above basal requirements, and will be maintained at that rate for the final 2 hours of the study (t=240-360).

**Plasma measurements:** From t=0 to t=360 min., blood samples will be obtained at hourly intervals for determinations of plasma glucose, insulin, glucagon, C-peptide, growth hormone, free fatty acids (FFA), glycerol, and lactate. Additional samples for D2G determinations will also be obtained every 15 min. Plasma glucose will be measured every 5-10 min in duplicate by a Beckman glucose analyzer. Plasma lipids (LDL, HDL, VLDL, total Cholesterol and Triglycerides) will be measured

at t=0.

**Biopsies:** From t=225-240 min, fat and muscle biopsies will be obtained. Participants will have fat biopsies performed in the periumbilical region. A small 0.5 cm cutaneous incision will be performed under local anaesthesia (Lidocaine 1% with Epinephrine) and 1-2 g of adipose tissue will be obtained by aspiration technique (79). A skeletal muscle biopsy will be obtained from vastus lateralis muscle using a cadence muscle biopsy needle following local anaesthesia extending into the muscle area. The total amount of muscle obtained will be ~300 mg. The biopsy specimens will be immediately homogenized in Trizol at the bedside, to inhibit any RNAase activity, and will subsequently be stored at -80 °C. Pressure will be applied at the biopsy site for ~10 min following the biopsy. A pressure bandage will be applied and kept on 5-6 hours after the biopsy. Since the biopsies are performed in 4 hours into the clamp and the subject will undergo direct observation for an additional 3-4 hours. The biopsy site will be examined prior to discharge and a pressure bandage will be reapplied for an additional two hours. Subjects will be able to remove the bandage once they get home.

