***These techniques are approved by the CCI under Protocols 2000-200 and 2006-414.***

**Aim 2: To examine the effects of resveratrol on systemic inflammation and/or on adipose tissue macrophages.**

This aim will make use of the **adipose biopsy specimens from Aim 1**. We will therefore examine the effects of resveratrol on macrophage content and activation in adipose tissue, and on systemic markers of inflammation, in **the same n=55 overweight, middle aged** (age 45-65) nondiabetic and diabetic subjects. We will be utilizing the younger 21-44 year old population to assess whether resveratrol has the same beneficial effects in younger subjects.

*We hypothesize that treatment of insulin resistant subjects with resveratrol will lead to reductions in systemic inflammatory markers and reduced content and/or activation of adipose tissue macrophages.* Systemic inflammatory markers to be measured will include TNF-a, IL-6, IL-1b, MCP-1. Adipose tissue macrophages will be isolated from subcutaneous abdominal adipose tissue, and will be quantified by fluorescence activated cell sorting (FACS) analysis. Gene expression of a variety of pro-inflammatory and pro-atherosclerotic factors will be examined by „real-time“ rt-PCR, to determine how resveratrol affects activation of adipose macrophages.

Following administration of resveratrol (n=55) for 28 days, we will examine:

1. Adipose macrophage content, by fluorescence activated cell sorting (FACS) analysis. These data will additionally be confirmed by immunohistochemistry
2. Activation of adipose macrophages, as assessed by expression and production of a variety of pro-inflammatory and pro-atherosclerotic factors, using „real-time“ rt-PCR and immunohistochemistry
3. Plasma levels of cytokines and acute phase reactants

**Adipose biopsy specimens-** Adipose biopsy specimens will be obtained as described above. Suctioned adipose tissue samples will be suspended in PBS and washed with a 40 µm cell strainer. Approximately 1 gram of tissue will be immediately homogenized in Trizol (Life Technologies, Bethesda, MD) with a Tissumizer homogenizer. This technique will ensure optimized yields of mRNA by the inhibition of RNases. The homogenate will be frozen on dry ice, transported to the laboratory and stored at -80°C. Subsequent mRNA extraction and analysis of gene expression will be performed in the Gene Expression Core lab. Remaining fresh adipose biopsy specimens will be immediately processed as described below.

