### **Aim 3: To explore the effects of resveratrol on skeletal muscle metabolism and function.**

*We hypothesize that resveratrol treatment will enhance mitochondrial metabolism and improve strength and contractility.* We will examine the effects of resveratrol on mitochondrial content, signaling molecules involved in mitochondrial biogenesis, DNA and protein oxidative damage, and mitochondrial respiration in human skeletal muscle. It is anticipated that mitochondrial ATP production and aerobic muscular function will improve in concert with enhanced insulin sensitivity.

This aim will make use of the **muscle biopsy specimens from Aim 1**. We will therefore examine the effects of resveratrol on muscle mitochondrial function and aerobic muscular function in **the same n=25 overweight, middle aged** (age 45-65) nondiabetic and diabetic subjects. Again, We will be utilizing the younger 21-44 year old population to assess whether resveratrol has the same beneficial effects in younger subjects.

Following administration of resveratrol (n=55) for 28 days, we will examine:

1. Muscle mitochondrial content
2. Muscle mitochondrial function
3. Muscle strength and mobility

**Muscle biopsies:** human skeletal muscle biopsies will be obtained as described above, and stored at -80 °C for analysis of the following:

- mitochondrial content
- signaling molecules involved in mitochondrial biogenesis
- DNA and protein oxidative damage, and
- mitochondrial respiration
- skeletal muscle mitochondrial function (citrate synthase and succinate dehydrogenase activity), content, and morphology by electron microscopy.

**Muscle strength and mobility tests:** will be conducted by our collaborators from the Department of Neurology and assess the following:

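### Muscle biopsies are given only a Trizol and −80 °C route, so Aim 3 electron microscopy has no stated fixed sample and respiration rests on an unnamed method

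*Combined protocol and SAP*

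**What the plan says.** The Biopsies paragraph, under In vivo clamp studies – General Conditions, takes both tissues in the same 15-minute window of the clamp. For fat, "1-2 g of adipose tissue will be obtained by aspiration technique". For muscle, "The total amount of muscle obtained will be ~300 mg". The next sentence applies to both: "The biopsy specimens will be immediately homogenized in Trizol at the bedside, to inhibit any RNAase activity", followed by storage at −80 °C. Muscle is not excepted.

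The muscle paragraph of the Aim 3 section refers back to this: "human skeletal muscle biopsies will be obtained as described above, and stored at" −80 °C. The assays listed for that material are mitochondrial content, biogenesis signalling, oxidative damage, respiration, and a final item that includes "citrate synthase and succinate dehydrogenase activity), content, and morphology by electron microscopy". The opening of the section also promises "DNA and protein oxidative damage, and mitochondrial respiration in human skeletal muscle". The Aim 3 paragraph of the Specific Aims lists respiration too. It names a Mitochondrial Metabolic Core as collaborator but says nothing about specimen handling.

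Fat is treated differently under Aim 2: "Approximately 1 gram of tissue will be immediately homogenized in Trizol", and then "Remaining fresh adipose biopsy specimens will be immediately processed as described below". The paragraphs that follow describe collagenase digestion of fat and fixation with paraffin embedding for immunohistochemistry.

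**The concern.** The Aim 3 assay list calls for tissue in different states, but the plan gives muscle one path. Homogenizing removes the structure that electron microscopy is meant to show, and freezing is not fixation. The documents do not state these tissue requirements; I take them from general laboratory knowledge and treat them as an assumption.

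The timing makes the gap matter. The Schedule of proposed clinical studies has muscle biopsies only on day 0 and day 28. If the day-0 specimen is handled in a way that rules out an assay, the baseline cannot be taken again once resveratrol has started, and that subject contributes no paired change for that measure.

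**Working it through.** The plan states no figure to reproduce. The check is a side-by-side reading of every section that describes biopsy handling or muscle assays, plus two small counts.

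| | Fat | Muscle |
|---|---|---|
| Amount taken | 1–2 g | ~300 mg |
| Trizol | about 1 g (Aim 2) | the specimens, no amount given (Biopsies paragraph) |
| Fresh portion | the remainder | none stated |
| Fixed portion | yes, for immunohistochemistry | none stated |
| −80 °C | Trizol homogenate | all listed assays (Aim 3) |

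**Tissue left outside Trizol.** Fat: 1 − 1 = 0 g at the lower yield and 2 − 1 = 1 g at the upper, so about 0 to 1 g. Muscle: 0 of ~300 mg is stated as fixed or fresh. The muscle figure counts what is written, not what the laboratory may do.

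**Two readings of the Trizol sentence.**

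- *Literal for muscle.* Everything is homogenized. Morphology is lost, and so are the two enzyme activities and any assay needing intact tissue.
- *Shorthand for the RNA portion.* The rest of the muscle goes to −80 °C, as Aim 3 says. Enzyme and protein assays then have a sample. Electron microscopy still has no fixed piece, because freezing is the only stated route. Respiration has a sample only if the laboratory's method accepts frozen tissue, and no method is named.

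The missing fixed sample for morphology is therefore common to both readings. The enzyme loss belongs only to the first. On the shorthand reading, the respiration loss depends on a fact the documents do not give.

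**Number of biopsies.** The Aim 3 section gives two subject counts: 25 where it introduces the middle-aged group, and 55 where it describes treatment. The Aim 1 section gives 40 + 15 = 55, and General Experimental Conditions expects all 55 in every study. With two visits each:

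- 25 × 2 = 50 biopsies
- 55 × 2 = 110 biopsies

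**The case against.** The strongest reply is that the Trizol sentence was never meant to cover all the tissue. It carries its own purpose, protecting RNA. Aim 2 shows that it is incomplete for fat, and Aim 3 describes muscle storage without mentioning Trizol. What remains could be called omitted bench detail that the collaborating core may hold in its own procedures. The Aim 2 paragraph on rt-PCR also mentions immunohistochemistry and Western blotting just after a sentence about muscle, which is at least consistent with some muscle being kept out of Trizol.

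Much of this stands. A reader might infer that all the muscle is destroyed at the bedside and that every mitochondrial measure fails. The documents do not support that, for the reasons just given. A reader might also infer that respiration is certainly lost. That does not follow either, because the assay is not named.

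The objection does not remove the morphology gap. Aim 3 is not silent on muscle: it assigns −80 °C storage to the material for electron microscopy, and no section adds a fixed piece. The core is named without any handling instruction, and the written step happens at the bedside, before a core would receive tissue. The immunohistochemistry remark states no muscle fixation and concerns neither electron microscopy nor respiration.

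**Conclusion.** The point holds in a limited form. Followed as written, the plan leaves electron-microscopy morphology of muscle without a fixed sample, whichever way the Trizol sentence is read. Respiration is at risk only if its method needs fresh tissue, and enzyme activities only if the Trizol sentence is literal for muscle.

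The reach is 50 to 110 biopsies. The upper figure should not be taken as settled, since the Aim 3 section itself gives both subject counts and they must be reconciled. Nor is it a forecast of losses: the harm falls subject by subject and ends once handling is corrected.

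It would also be wrong to infer damage to the main result. The principal endpoint is whole-body glucose uptake in the final hour of the high-insulin phase, which uses no biopsy tissue. RNA measures and the strength and mobility tests are likewise untouched. Aim 3 is worded as exploratory. I rate this minor to moderate: narrow in scope, but irreversible for a subject whose baseline specimen is lost, and cheap to prevent.

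**What to change.** 1. In the Biopsies paragraph, limit the Trizol sentence to the portion of each specimen intended for RNA.
2. In the Aim 3 muscle paragraph, state that from the same ~300 mg one piece is fixed at the bedside for electron microscopy and one is frozen at −80 °C without Trizol for enzyme and protein assays.
3. Set one allocation and one priority order, with masses taken from the laboratory's assay minimums, and apply both unchanged on day 0 and day 28 so that the paired comparison is preserved.
4. For respiration, name the method and the tissue state it needs. Otherwise remove the measure from both the Specific Aims and the Aim 3 section; removing it from one alone would create a new inconsistency.
5. If the immunohistochemistry sentence in the rt-PCR paragraph is meant to include muscle, list that use in the allocation.
6. Reconcile the subject counts of 25 and 55 in the Aim 3 section.

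The cost is wording and a few extra tubes per biopsy, with no additional biopsy. The downside is less muscle for RNA. The documents give no assay minimums, so it is unknown whether ~300 mg covers every use; if it does not, the priority order decides what is dropped. A fresh-tissue respiration method would also need laboratory capacity on each clamp day, which the documents do not describe.

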**Glucose Kinetics-** Plasma for labeled glucose radioactivity will be treated as previously described (86). Rates of glucose appearance (Ra) and disappearance (Rd) and other indices of glucose turnover will be estimated by using the steady-state equation of Steele (87). Endogenous glucose production (EGP) will be determined by subtracting the rates of glucose infusion from the tracer-derived rate of appearance of glucose. Data for glucose turnover represent the mean values during the final 60 min of the low insulin period (t=60-120 min), and during the final 60 min of the hyperglycemic period (t=180-240 min).

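### The glucose-turnover averaging windows do not match the clamp timetable, and neither covers the hour that defines the principal endpoint

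*Combined protocol and SAP*

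**What the plan says.** All of the relevant text is in the combined protocol and SAP.

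- **Clock origin.** In the clamp General Conditions, the tracer infusion "will be initiated at t=-120 min (2 hours prior to the onset of the" clamp, so t=0 is clamp onset.
- **Basal phase.** "From t=0 min to t=120, optimal insulin infusion rates will be selected" for each subject, the target being the rates "required to maintain euglycemia (90 mg/dl) without the requirement for exogenous glucose infusion".
- **Low phase.** Insulin is raised by 20 mU/m²/min at t=120 and "will be maintained at this rate for 2 hours (T=120-240").
- **High phase.** Insulin goes to 80 mU/m²/min above basal at t=240 and "will be maintained at that rate for the final 2 hours of the study (t=240-360").
- **Glucose target.** "Throughout the entire 360 min the plasma glucose concentration will be maintained at basal levels", about 90 mg/dl.
- **Averaging rule.** Glucose Kinetics says that the turnover data are means over "the final 60 min of the low insulin period (t=60-120 min), and during the final 60 min of the hyperglycemic period (t=180-240 min").
- **Endpoints.** Aim 1 defines hepatic insulin action as suppression of glucose production in the low phase, and peripheral insulin action as glucose uptake in the high phase. Statistical Analysis makes whole-body glucose uptake in the last hour of the high insulin clamp the principal endpoint, compared before and after treatment by paired t-test.

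**The concern.** Glucose Kinetics is the only place in the text that gives clock times for averaging turnover. Its times disagree with the phase boundaries, and one of its labels names a phase that this design does not have.

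Two measures are affected. The hepatic measure would be taken from an hour in which insulin is being titrated, about every 25 minutes, so that no exogenous glucose is needed. That hour shows basal glucose production, not suppression by the 20 mU/m²/min step, and a steady-state equation would be applied to it. The principal endpoint needs the 80 mU/m²/min hour, for which the paragraph gives no window. The second window, where a reader would look for the high-insulin result, is in fact the low-phase hour. An analyst who took it as the high-insulin value would enter a different quantity into the principal paired test from one who worked from the phase description and Statistical Analysis.

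**Working it through.** **Inputs.** Phases, from the clamp General Conditions: basal 0-120, low 120-240, high 240-360 min. Windows, from Glucose Kinetics: W1 = 60-120 (labelled low insulin) and W2 = 180-240 (labelled hyperglycemic).

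**Step 1: final hour of each phase** (end of phase minus 60 min).
- Basal: 120 − 60 = 60, giving 60-120.
- Low: 240 − 60 = 180, giving 180-240.
- High: 360 − 60 = 300, giving 300-360.

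**Step 2: overlap of the stated windows with those hours**, as max(0, earlier end − later start), in minutes.

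| Window | Basal 60-120 | Low 180-240 | High 300-360 |
|---|---|---|---|
| W1, 60-120 | 60 | 0 | 0 |
| W2, 180-240 | 0 | 60 | 0 |

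The stated times therefore do not reproduce the labelled periods. W1 is exactly the last basal hour and W2 exactly the last low-phase hour. If labels are ignored, the low-phase hour is averaged in full (60 of 60 min) and the high-phase hour not at all (0 of 60).

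**Step 3: insulin increment above basal in each window.** W1: 0, where the label implies 20 mU/m²/min. W2: 20, where the second step of the clamp is 80.

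**Step 4: could the paragraph use another clock?** Add 120 min, so that its zero is the start of the low phase: 60-120 becomes 180-240 and 180-240 becomes 300-360. Both windows then fit exactly and only the hyperglycemic label is wrong. Subtracting 120 min fits neither label. Checking the +120 clock against the other timed steps:
- The tracer starts at t=−120, described as two hours before onset, so onset is t=0.
- Biopsies are at t=225-240, with the remark "Since the biopsies are performed in 4 hours into the clamp"; 240 min is 4 hours from t=0. On the +120 clock they would fall at 345-360, close to 6 hours in.
- Indirect calorimetry is at T=260-280. On the +120 clock it would fall at 380-400, after all infusions stop at t=360.

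No other timed step uses the +120 clock, and Glucose Kinetics does not announce one.

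**Step 5: tracer duration (secondary).** The tracer starts at t=−120. The General Conditions say that it runs for the whole study and also give a total of 6 hours.
- 6 hours counted from the start: −120 + 360 = 240, which covers 0 of the 120 high-phase minutes.
- Running until all infusions stop at t=360: 360 − (−120) = 480 min = 8 hours, which covers 120 of 120.

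**The case against.** The strongest reply is that the plan identifies the right hours in words. Statistical Analysis names the final hour of the high insulin clamp, the clamp description puts that phase at t=240-360, and t=300-360 follows. Likewise the averaging sentence speaks of the low insulin period, which the clamp description defines as t=120-240; only the times in parentheses disagree. No window is labelled high insulin, so nothing instructs an analyst to report t=180-240 as the principal endpoint. The paragraph also reads like text carried over from another design: it mentions labelled-glucose radioactivity, although Potential Risks calls the tracer non-radioactive. This points to a drafting slip.

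Much of that is fair. The principal endpoint is not undefined, and misuse of the second window is a risk of misreading, not an instruction. But a carried-over sentence is still the only stated averaging rule. Its explicit times are what a programmer would code, and they give a wrong hepatic value and no high-phase value.

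Two further points stand as limits. The clamp section contains a figure that was not available for this review, so the statement that no second clock is given holds for the text only. And the 6 hours quoted for the tracer may mean the 360-minute clamp without the two-hour lead-in, in which case the infusion would run to t=360. That is why the tracer point is secondary.

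**Conclusion.** The averaging rule is wrong as written and must be corrected before turnover is computed. On the stated clamp clock, each window misses the period that its label or position implies by the full 60 minutes, and the principal-endpoint hour is not covered at all. The size of the resulting error in glucose production or uptake cannot be worked out from the documents; in terms of insulin exposure it is 0 against 20, and 20 against 80, mU/m²/min above basal.

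The conclusion rests on taking t=0 as clamp onset, which every other timed step supports. If the authors meant a clock starting at the low phase, the timing error vanishes and what remains is an unstated origin and a wrong label. The tracer duration is an unresolved inconsistency whose effect on the high-phase measurement ranges from none to complete loss of tracer coverage, depending on the reading.

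**What to change.** Replace the averaging sentence in Glucose Kinetics with one on the clamp clock, for example: *Glucose turnover will be averaged over the last 60 min of the low insulin phase (t=180-240 min; hepatic insulin action) and the last 60 min of the high insulin phase (t=300-360 min; principal endpoint), where t=0 is the start of the basal phase.* Remove the reference to a hyperglycemic period. If t=60-120 is also reported, label it basal.

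This costs one sentence and adds no procedure. Tracer samples are scheduled every 15 min; assuming that they follow the t=0-360 range given for the other plasma samples, (360 − 300)/15 + 1 = 5 samples already fall in the principal-endpoint window.

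Separately, the investigators should reconcile the 6-hour tracer duration with the statements that the tracer runs for the whole study and that all infusions stop at t=360, so that the written schedule supports the high-phase measurement. Which duration stands is for them to decide, and the cost depends on their answer.
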